8.3.3.3 Duration of corticosteroids treatment for irAE during avelumab plus axitinib treatment

Analysis set	Analysis population
Details of analysis	Perform the same analysis as in 8.3.3.2 for duration of corticosteroid treatment.
Supplement	If the patient is on continuous corticosteroid treatment, the period should be up to the cut-off date (20 June, 2021).

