### **8.2. Secondary objectives**

- 1) To evaluate the efficacy of avelumab plus axitinib combination therapy for patients with mRCC treated in Japan.
- 2) To describe clinical usage of corticosteroid for immune-related adverse events (irAE) during avelumab plus axitinib combination therapy period.
- 3) To describe pre-treatment and treatment for infusion-related reaction of avelumab.
- 4) To describe patterns of post progression subsequent treatments.

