### **9.1.2. Secondary endpoints**

- Efficacy endpoint
  - Time to treatment failure (TTF) of avelumab plus axitinib as a first-line therapy
  - Real-world PFS
  - Objective response (OR)
- Avelumab-related endpoints
  - TTF
  - Discontinuation and interruption of avelumab
  - Reason for discontinuation and interruption
- Axitinib-related endpoints
  - TTF
  - Dose increase, dose reduction, discontinuation, and interruption of axitinib
  - Reason for dose increase, dose reduction, discontinuation, and interruption
- Corticosteroid-related endpoints
  - Cumulative dose of corticosteroid for irAE during avelumab plus axitinib treatment
  - Duration of corticosteroid treatment for irAE during avelumab plus axitinib treatment
  - Number of corticosteroid administrations for irAE during avelumab plus axitinib treatment
- Infusion-related reaction-related endpoints

- Presence of pre-medication for potential infusion-related reaction of avelumab
- Drugs of pre-medication for infusion-related reaction of avelumab
- Presence of treatment for infusion-related reaction of avelumab
- Subsequent treatment-related endpoints
  - Drugs used after avelumab plus axitinib

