### **9.2.1. Inclusion criteria**

Patients must meet all of the following inclusion criteria to be eligible for inclusion in the study:

- 1) Diagnosed with mRCC based on the General Rule for Clinical and Pathological Studies on Renal Cell Carcinoma (4th Edition) before receiving avelumab plus axitinib as a first-line therapy;
- 2) Over 20 years of age at the time of mRCC diagnosis;
- 3) Start treatment with avelumab plus axitinib as a first-line therapy for mRCC from 20 December 2019 to 20 December 2020;
- 4) For patients who are still alive and have routine visits to the study site, evidence of a personally signed and dated informed consent document indicating that the patient has been informed of all pertinent aspects of the study. For patients who are still alive and had been transferred to another hospital, evidence that the patient has been informed of all pertinent aspects of the study and oral or written informed consent is obtained.
- 5) Deceased patients are also included for inclusion criteria 1-3.

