### **9.3.7. Corticosteroid treatment**

The following corticosteroid treatment data for irAE will be collected: date of treatment, drugs of corticosteroid, dose of corticosteroid, cumulative dose of corticosteroid, duration of treatment, and number of administrations during the treatment with avelumab plus axitinib.

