8.3.3 Corticosteroid-related endpoints

8.3.3.1 Corticosteroid treatment for irAEs during avelumab plus axitinib treatment

Analysis set	Analysis population
Details of analysis	Tabulate the number of patients treated for irAE with corticosteroids. Presence of high-dose corticosteroids treatment (prednisolone equivalent of 40 mg or more) will also be tabulated.

8.3.3.2 Cumulative corticosteroids dosages for irAEs during avelumab plus axitinib treatment or monotherapy

Analysis set	Analysis population
Details of analysis	Calculate summary statistics of corticosteroids dosing information for irAE. The dosages to be tabulated are prednisolone equivalents.

	Presence of high-dose corticosteroids treatment (prednisolone equivalent of 40 mg or more) will also be tabulated.
Supplement	If the same patient received multiple doses of corticosteroids, each dose should be tabulated separately (including patients who received multiple doses of the same corticosteroid).

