8.3.6 Outcome information

Analysis set	Analysis population
--------------	---------------------

Details of analysis	Tabulate the duration from the date of initial dose to the date of last confirmation of survival (or date of death in the cases of death), with the cause of death and the reason for lost to follow-up. In addition, tabulate the status of the first-line treatment and the reason for its discontinuation if the treatment has been discontinued.
---------------------	---

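### SAP 8.3.3.3 runs a continuing corticosteroid course to 20 June 2021 with no cap at death or last chart record, and does not apply the endpoint's treatment window

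*SAP*

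**What the plan says.** **The rule.** The Supplement to SAP 8.3.3.3 reads: "If the patient is on continuous corticosteroid treatment, the period should be up to the cut-off date (20 June, 2021". The analysis is defined by reference: "Perform the same analysis as in 8.3.3.2 for duration of corticosteroid treatment". That means plain summary statistics with repeated courses in one patient tabulated separately, and no censoring method.

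**The window.** Three protocol sections tie steroid use to the combination period:
- the second secondary objective (8.2): "To describe clinical usage of corticosteroid for immune-related adverse events (irAE) during avelumab plus axitinib combination therapy period"
- the endpoint (9.1.2): "Duration of corticosteroid treatment for irAE during avelumab plus axitinib treatment"
- the data to be collected (9.3.7): "duration of treatment, and number of administrations during the treatment with avelumab plus axitinib"

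The title of SAP 8.3.3.3 repeats this limit. The title of SAP 8.3.3.2, whose analysis 8.3.3.3 borrows, is wider: "Cumulative corticosteroids dosages for irAEs during avelumab plus axitinib treatment or monotherapy". SAP 9 declares no changes from the protocol.

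**Who is in the data.** Protocol 9.2.1 states: "Deceased patients are also included for inclusion criteria 1-3". It also admits living patients who have moved to another hospital. SAP 8.3.6 tabulates outcome times "with the cause of death and the reason for lost to follow-up".

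**How other durations end.** Real-world PFS is censored at the last visit or at the start of next-line therapy (Protocol 9.1.3.2). SAP 6.3 uses the last progression-free confirmation, and SAP 8.3.6 uses death or the last date known alive. All of these are patient-specific dates.

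**The concern.** The word *continuous* is not defined, and the end date is one calendar date for everybody. A chart may show a steroid course as continuing at its last entry, with no stop date, because the patient then died, transferred or was lost. Taken literally, the rule carries that course to 20 June 2021. The check in SAP 6.1 would not catch this: it rejects only imputed dates that reverse the order of start and end, and here the order is preserved.

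Separately, a patient can stop avelumab and axitinib and stay on steroid. The rule then counts days after combination treatment in an endpoint whose title limits it to that treatment, while cumulative dose is summarised over a window that also names monotherapy.

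At stake is a named secondary endpoint. About 70 patients are expected in total and the number who will have steroid courses is not given, so a few very long durations could shape the table.

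**Working it through.** The documents give no figure for this endpoint, so there is nothing to reproduce. The check is date arithmetic.

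**Inputs from the documents.** Index dates run from 20 December 2019 to 20 December 2020 and the observation period ends on 20 June 2021 (Protocol 9.1). One month is 30.4375 days (SAP 6.2).

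**Assumptions.** Duration = end − start + 1; SAP 6.3 gives formulas for avelumab, axitinib and non-administration but none for corticosteroid. Steroid start dates, end dates and numbers of affected courses are illustrative.

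**Step 1: upper bound for one course.** A course that starts on or after index and is wrongly carried to cut-off gains at most the index-to-cut-off span.
- Index 20 December 2019: 366 + 182 = 548 days; 548 / 30.4375 = 18.0 months.
- Index 20 December 2020: 182 days; 182 / 30.4375 = 6.0 months.

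**Step 2: illustrative courses.** Assume steroid starts 60 days after index, and that death or the last record comes 30 to 90 days after that with no recorded stop. The capped duration is then 31 to 91 days.

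| Index date | Steroid start | Days under the rule | Days if capped | Excess, days | Excess, months |
|---|---|---|---|---|---|
| 20 Dec 2019 | 18 Feb 2020 | 489 | 31 to 91 | 398 to 458 | 13.1 to 15.0 |
| 20 Jun 2020 | 19 Aug 2020 | 306 | 31 to 91 | 215 to 275 | 7.1 to 9.0 |
| 20 Dec 2020 | 18 Feb 2021 | 123 | 31 to 91 | 32 to 92 | 1.1 to 3.0 |

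**Step 3: effect on the summary.** Shift in mean = affected courses × excess / courses summarised. The unit is the course, because 8.3.3.2 tabulates repeated courses separately. With 1 to 5 courses affected by 60 to 360 days each:
- 10 courses: 1 × 60 / 10 = 6 days up to 5 × 360 / 10 = 180 days
- 20 courses: 1 × 60 / 20 = 3 days up to 5 × 360 / 20 = 90 days
- 30 courses: 1 × 60 / 30 = 2 days up to 5 × 360 / 30 = 60 days

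Among 20 values, one to three extreme ones occupy ranks 18 to 20. The third quartile lies at about ranks 15 to 16. They therefore set the maximum but not the third quartile, which can move only by a few ranks.

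**Step 4: the window.** Suppose steroid starts on 20 April 2020, both drugs stop on 1 May 2020 and the steroid continues past cut-off. Days during combination treatment: 20 April to 1 May = 12. Days under the rule: 20 April 2020 to 20 June 2021 = 427. The two readings differ by 427 − 12 = 415 days for the same course.

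**Step 5: the opposite direction.** A course truly ongoing on 20 June 2021 is cut at that date, yet the summary statistics treat it as complete. Its full length is understated.

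**The case against.** The strongest reply is that the SAP sentence does not mention patients who died or left. Its ordinary meaning is a course still running at data cut-off, and a patient who died in 2020 is not on treatment in June 2021. Treatment dates and duration are collected from the chart (Protocol 9.3.7), queries and remote monitoring can resolve inconsistent records (9.6 and 9.8), and data on transferred patients can be obtained from the other facility (10.2.2). A careful programmer would probably end a course at death. This stands as a limit on the point: the defect is a missing cap, not an instruction to count days after death. It does not remove the need for the cap, because a prespecified rule should not depend on the programmer's guess.

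On the window, the endpoint can also be read as steroid treatment for irAEs that arise during therapy, followed to the end of the course. On that reading the 427 days in Step 4 are not an error. This stands too. The documents do not say which reading applies, and 8.3.3.2 names a further window.

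A reader might also infer three stronger claims that the documents do not support:
- **That steroid duration is overstated overall.** Courses truly ongoing at cut-off are truncated. For a transferred patient with an unknown stop, the true end may fall before or after cut-off. The net direction is not known.
- **That dose and duration for one course must disagree.** SAP 8.3.3.2 is silent on how dose is handled for a continuing course.
- **That the on-treatment window is the only valid endpoint.** The alternative reading above is possible.

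**Conclusion.** The point holds as a gap in a stated rule. With no cap at death or last chart record, SAP 8.3.3.3 can credit a course with days after death or days that nobody observed, by up to 182 to 548 days depending on the index date. The illustrative excess is 32 to 458 days per affected course. The effect would fall mainly on the mean and maximum: 3 to 90 days on the mean if 20 courses are summarised and 1 to 5 of them are affected by 60 to 360 days. Those counts are assumptions, so no net bias can be stated.

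The window is a separate inconsistency that rests on the text alone: the protocol and the title of 8.3.3.3 name combination treatment, 8.3.3.2 adds monotherapy, and the end-date rule applies neither. Severity is minor to moderate, because this is a descriptive secondary endpoint in a study that tests no hypothesis.

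**What to change.** Replace the Supplement in SAP 8.3.3.3 with a rule to this effect:
- A course with no recorded stop ends at the earliest of death, last chart record and 20 June 2021.
- The table states how many courses were still open at the last record or at cut-off, since those durations are truncated. Courses ended by death are counted separately.
- Steroid dose and duration use one stated window. Days during avelumab plus axitinib treatment are shown beside full course length, so neither reading is lost.

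The window needs a stated end for patients who stop one drug before the other, because SAP 6.3 leaves this at and/or and 8.3.3.2 admits monotherapy. If the wider window is kept, SAP 9 should record it as a change from the protocol.

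The cost is a short SAP revision and a few lines of programming. Death and last-contact dates are already needed for SAP 8.3.6, and treatment-end dates for SAP 6.3. The downside is that some reported durations become shorter, and a course capped at the last record may have continued elsewhere, which is why the count of open courses belongs in the table.

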8.3.3.4 Number of corticosteroid administrations for irAEs during avelumab plus axitinib treatment

Analysis set	Analysis population
Details of analysis	Perform the same analysis as in 8.3.3.2 for the number of corticosteroid administrations.
Definition	Number of doses: the number of times treatment has been given, counting "treatment start to treatment end" as one dose.

8.3.4 Endpoints for infusion-related reaction

Analysis set	Analysis population
Details of analysis	Tabulate presence of avelumab treatment for infusion-related reactions, as well as presence of prior therapies and names of drugs.

8.3.5 Subsequent treatment-related endpoints

Analysis set	Analysis population
Details of analysis	Calculate summary statistics by drug for duration of subsequent treatment following avelumab plus axitinib treatment.

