#### **9.1.3.2. Real-world PFS**

Real-world PFS is defined as the following:

- Real-world PFS, defined as time from start of avelumab/axitinib treatment to date of first disease progression (as clinically assessed by local investigator based on radiology, laboratory evidence, pathology, or other assessments) or death due to any cause, whichever came first  
If there were no clinical records of death or disease progression, they were censored at the date of initiation of the next line of therapy for the patients undertaking two or more lines of therapy based on the record, or at their last visit date during the study period for the patients undertaking only one line of therapy based on the record.

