### **9.3.9. Second-line regimen after avelumab plus axitinib treatment**

The following second-line regimen data will be collected: medication after avelumab plus axitinib treatment.

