6 DATA HANDLING

6.1 Handling of omitted or missing data

- If date data is missing, it will be handled as follows:
 - If "year" is unknown, it will be treated as missing.
 - If "month" is unknown, July will be used.
 - If "date" is unknown; 15th will be used
 - If "month and date" are unknown, 1st July will be used.
- Except as noted above, missing values will not be supplemented.

- If the above supplementation results in reversal of days in the calculation of the number of days (e.g., the number of days from the start of treatment to the end of treatment), it will not be adopted in the analysis.

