6.3 Derivation variables

1) Survival time analysis

It is defined as follows:

Endpoint	Start date	End date (event)	End date (censor)
Real-world PFS	Date treatment with avelumab and/or axitinib was initiated (if not on the same day, whichever occurs earlier)	Date of first disease progression (clinical evaluation based on radiological, laboratory, pathological, or other evaluation by the principal investigator) or death from any cause, whichever occurs earlier	Date of last confirmation of progression-free survival or start of subsequent treatment (whichever occurs earlier)
TTF of avelumab and axitinib	Date treatment with avelumab and/or axitinib was initiated	Date of completion of treatment with avelumab and/or axitinib	Date of last confirmation of progression-free survival or date of last dose in case of efficacy stopping (whichever date occurs earlier)
TTF of avelumab	Date treatment with avelumab was initiated	Date of completion of treatment with avelumab	Date of last confirmation of progression-free survival or date of last dose in case of efficacy stopping (whichever date occurs earlier)
TTF of axitinib	Date treatment with axitinib was initiated	Date of completion of treatment with axitinib	Date of last confirmation of progression-free survival or date of last dose in case of efficacy stopping (whichever date occurs earlier)

2) Objective response rate

ORR is defined as the proportion of patients with a CR or PR as the best overall response in tumor assessment during the observation period, as assessed by an investigator under actual clinical practice, including assessment based on RECIST ver. 1.1.

3) Calculation of duration

Duration	Definition
Duration of avelumab treatment	Date of last dose – date of initial dose + 14
Duration of axitinib treatment	Date of last dose – date of initial dose + 1
Duration of non-administration	Date of end – Date of start + 1

4) Corticosteroid equivalent dose (prednisolone equivalent)

This will be calculated as shown in the table below.

Generic name	Corresponding amount (mg)	Prednisolone conversion ratio
Cortisone	25	0.2
Hydrocortisone	20	0.25
Prednisolone	5	1
Methylprednisolone	4	1.25
Triamcinolone	4	1.25
Dexamethasone	0.75	6.7
Betamethasone	0.6	8.3

5) Date of initial dose

If avelumab and axitinib are administered for different durations, the earlier of the two dates should be used as the date of the initial dose.

6) Date of last confirmation of progression-free survival

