7.2 Summary statistics

Summary statistics for continuous variables will be calculated for observed and missing values, mean, median, standard deviation, minimum, maximum, first quartile, third quartile, etc.

Summary statistics for categorical variables will be calculated for frequency and proportion.

Other statistics, if calculated, will be described separately.

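### SAP 8.3.5 summarises duration of subsequent treatment with plain statistics and no rule for courses still running at the 20 June 2021 cut-off, so reported durations will be too short

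*SAP*

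**What the plan says.** SAP 8.3.5 consists of an analysis set and one instruction: "Calculate summary statistics by drug for duration of subsequent treatment following avelumab plus axitinib treatment". Unlike several neighbouring sections, it has no definition or supplement row.

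The general rule it falls back on is SAP 7.2: "Summary statistics for continuous variables will be calculated for observed and missing values, mean, median, standard deviation", followed by range and quartiles. SAP 6.1 gives imputation rules for partial dates, treats a date with unknown year as missing, and adds: "Except as noted above, missing values will not be supplemented".

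SAP 6.3 defines durations for avelumab, axitinib and non-administration only. Its censoring table covers real-world PFS and the three TTF endpoints only. The one rule for treatment still running at cut-off is in SAP 8.3.3.3; it runs the period to 20 June 2021 and concerns corticosteroids.

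In the protocol, the objective is "To describe patterns of post progression subsequent treatments" (8.2), the endpoint is "Drugs used after avelumab plus axitinib" (9.1.2), and the data item is "The following second-line regimen data will be collected: medication after avelumab plus axitinib treatment" (9.3.9). SAP section 9, on changes from the protocol, is marked not applicable.

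**The concern.** First-line and subsequent treatment share one observation window that closes on a fixed calendar date. A patient who leaves first line late has little time left in which a subsequent course can be seen to end. Short courses are seen whole, while long ones are cut or lost. A plain mean or median then partly measures how much calendar time was left.

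First line has protection against this: the plain duration in SAP 8.3.2 stands beside Kaplan-Meier TTF in 8.3.1.1, 8.3.1.4 and 8.3.1.5. Subsequent treatment has no such counterpart. A reader of the report could take the tabulated durations as how long these drugs are given after avelumab plus axitinib, when they are lower than the truth by an unknown amount.

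There is also a mismatch of scope. The protocol asks which drugs were used; the SAP plans how long they were used, from a data list that names no second-line stop date, and records no change.

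**Working it through.** The plan states no figure for this analysis, so there is nothing to reproduce. The direction follows from the text; the size can only be illustrated.

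**Direction.** Let D be the true duration and W the time from start of the course to cut-off.
- Truncation reports min(D, W), which never exceeds D and is below it for every ongoing course.
- Completed-only reports D given D ≤ W, which selects the shorter courses.

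Both are biased short whenever any course is ongoing.

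**Follow-up (documents).** The index window is 20 December 2019 to 20 December 2020 and cut-off is 20 June 2021: 182 to 548 days. At 30.4375 days per month (SAP 6.2), a = 182/30.4375 = 5.98 and b = 548/30.4375 = 18.00 months. This covers both lines together. Expected size is about 70 patients.

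**Assumed, not in the documents.** Uniform accrual; exponential times; every patient who stops first line starts the next drug at once; first-line median 13.8 months (the trial PFS cited in protocol section 7, used as a proxy); true second-line median 6 months.

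**Starters and share ongoing.** With λ = ln 2/13.8 = 0.0502, μ = ln 2/6 = 0.1155 and M(r) = (e^(−ra) − e^(−rb)) / (r(b − a)):
- M(λ) = 0.556 and M(μ) = 0.271.
- Probability of leaving first line before cut-off = 1 − M(λ) = 0.444; 70 × 0.444 = 31 patients.
- Probability of having started and still being on the course at cut-off = λ(M(μ) − M(λ))/(λ − μ) = 0.219.
- Share of courses ongoing = 0.219/0.444 = 49%.

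**Medians (simulation, 2,000,000 patients, same inputs).** Months:

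| True median | Ongoing | Truncated | Completed only | Kaplan-Meier |
|---|---|---|---|---|
| 3 | 30% | 2.3 | 2.0 | 3.0 |
| 6 | 49% | 3.6 | 2.8 | 6.0 |
| 9 | 61% | 4.3 | 3.2 | 9.0 |
| 12 | 68% | 4.8 | 3.4 | 12.0 |

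At a true 6 months the shortfall is 1 − 3.6/6 = 40% if truncated and 1 − 2.8/6 = 53% if completed only. Across first-line medians of 7.2 to 20 months and true second-line medians of 3 to 12 months, the ongoing share is 27% to 69% and the direction does not change.

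**Is Kaplan-Meier's recovery built in?** Yes, when the two lines' times are independent. With correlations of 0.3, 0.5 and −0.3 between them, Kaplan-Meier stayed within 6% of the true median among starters; truncated medians were 32% to 45% short and completed-only medians 43% to 56% short.

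**By drug.** In groups of 10 (first-line median 13.8, true 6), 95% of truncated medians lie between about 1.4 and 6.6 months, and 94% fall below 6. The Kaplan-Meier median is not reached in about 15% of such groups; where it is reached, it ranges from about 2 to 12 months.

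**Data.** The start of the next line is already needed for PFS: the protocol says of patients without an event that "they were censored at the date of initiation of the next line of therapy", and SAP 6.3 censors at "Date of last confirmation of progression-free survival or start of subsequent treatment (whichever occurs earlier". Neither document lists a second-line stop date or an ongoing flag.

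**The case against.** The best defence is that this is a descriptive study of about 70 patients, that the duration is not a listed endpoint, and that per-drug groups will be too small for any median to mean much. Much of this stands. It is why the point is minor, and why per-drug Kaplan-Meier curves are not the remedy: at 10 patients the truncated range still includes the true value, and the Kaplan-Meier range is very wide. It does not remove the bias in the pooled figure or make a plain median interpretable.

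A reader might infer more than the documents support:
- *That no count of subsequent drugs is planned.* Protocol 9.7.2 and SAP 7.2 make frequency and percentage the default for categorical variables, and table layouts sit in a separate document (SAP section 1). What is missing is the denominator.
- *That ongoing courses will be dropped.* This is one reading of SAP 6.1, which deals with omitted or missing dates. A course that has not ended is arguably neither, and the corticosteroid rule points to truncation. If courses were lost as missing, 7.2 would show the missing count.
- *That the size of the bias is known.* No document gives second-line duration, uptake or time to next treatment, and 13.8 months is trial PFS, not treatment time.
- *That drugs will be wrongly ranked.* On the same inputs the truncated median is 5.3 months if first line stopped before 3 months and 2.4 if it stopped at 6 months or later. This separates drugs only if drug choice depends on when first line stopped, which neither document says.
- *That the duration cannot be computed.* Protocol 9.3.9 lists only the medication, but the eCRF is not available here and may hold more.

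**Conclusion.** The concern holds as a minor point on a secondary, descriptive output. SAP 8.3.5 leaves the duration of subsequent treatment undefined and has no rule for courses running at cut-off, and either way of filling the gap with plain statistics reports durations that are too short. The direction needs no assumption beyond some courses being ongoing; the size rests wholly on the assumptions listed above and should be quoted only as an illustration. The added duration analysis also departs from the protocol endpoint without being recorded in SAP section 9, and its data requirement is unconfirmed. The primary objective is unaffected.

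**What to change.** In SAP 8.3.5:
1. Define the duration of second-line treatment and report the number of courses ongoing at cut-off.
2. Estimate it by Kaplan-Meier pooled over drugs. The event is stopping for any cause, including death, in line with the protocol's TTF definition; ongoing courses are censored at the earlier of last contact and 20 June 2021. By drug, give n, number ongoing and observed range, labelled as observed to cut-off, with a Kaplan-Meier median only where numbers allow.
3. Confirm that second-line stop date and ongoing status are collected. If they are not, drop the duration analysis. If it stays, list it in SAP section 9 as an addition to the protocol.
4. As a clarification, state that the count and percentage of subsequent drugs use patients who stopped first-line therapy as the denominator. SAP 8.3.6 already tabulates first-line status.

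Extending the corticosteroid rule to second line would make handling uniform but keep the bias.

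The cost is SAP wording, reuse of the 8.3.1.1 code, and a check of two data items before the lock planned for 31 January 2022. The downside is that per-drug medians will be imprecise or not reached (about 15% of groups of 10 on the assumed inputs).

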5.2 Analysis population

Enrolled patients who meet all the inclusion criteria.

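### Objective 4 concerns treatment after progression, but the endpoint and SAP 8.3.5 take any later drug and do not separate patients by progression status

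*SAP*

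**What the plan says.** **Objective.** Protocol 8.2, item 4: "To describe patterns of post progression subsequent treatments". SAP section 4 repeats it unchanged.

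**Endpoint.** Protocol 9.1.2 lists "Drugs used after avelumab plus axitinib", with no reference to progression.

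**Variable.** Protocol 9.3.9 collects "medication after avelumab plus axitinib treatment", again without reference to progression.

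**Analysis.** SAP 8.3.5: "Calculate summary statistics by drug for duration of subsequent treatment following avelumab plus axitinib treatment". The named analysis set is the Analysis population, defined in SAP 5.2 as "Enrolled patients who meet all the inclusion criteria". Neither document defines a subset of progressed patients.

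**PFS censoring.** Protocol 9.1.3.2: "If there were no clinical records of death or disease progression, they were censored at the date of initiation of the next line of therapy". SAP 6.3 gives the censoring date for real-world PFS as "Date of last confirmation of progression-free survival or start of subsequent treatment (whichever occurs earlier").

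**Discontinuation reasons.** SAP 8.3.2 and 8.3.6 tabulate why first-line treatment stopped. Neither crosses the reason with the drug given next. SAP section 9 declares no changes from the protocol.

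**The concern.** The objective asks what is given once the combination has failed. The table describes what is given after the combination, whatever the reason for leaving it. The two coincide only if every patient who starts a later drug has progressed first, and the PFS censoring rules show that the authors did not assume this.

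At stake is whether objective 4 can be answered from the planned output. A description of post-progression patterns needs at least two things: which regimens progressed patients received and how often, and how many progressed patients received nothing further. A summary of durations by drug, pooled over reasons for switching, gives neither.

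**Working it through.** **1. Trace the condition from objective to table.**

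| Step | Place | Conditional on progression? |
|---|---|---|
| Objective 4 | Protocol 8.2, SAP 4 | Yes |
| Endpoint | Protocol 9.1.2 | No |
| Variable | Protocol 9.3.9 | No |
| Analysis set | SAP 8.3.5 with 5.2 | No |
| Statistic | SAP 8.3.5 | No; duration by drug only |

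The condition is lost at the endpoint and does not return.

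**2. Do the documents expect patients who break the link?** Yes. A rule that censors PFS at the start of the next line, for patients with no recorded progression or death, has a purpose only if such patients may exist. They fall outside objective 4 as worded but contribute a duration to SAP 8.3.5.

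**3. Does another table supply the split?** No. SAP 8.3.2 and 8.3.6 give discontinuation reasons on their own, not by next drug.

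**4. Size.** The plan has no figure to reproduce; protocol 9.5 says sample size calculations do not apply. The following is illustrative.

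Inputs from the documents:
- about 70 patients (protocol 9.5);
- index dates 20 December 2019 to 20 December 2020 and cut-off 20 June 2021, so 6 to 18 months of follow-up (protocol 9.1);
- median PFS 13.8 months, lower 95% limit 11.1, from the phase 3 trial cited in protocol 7.

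Assumptions: uniform entry, exponential PFS, no loss to follow-up before cut-off.

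With λ = ln 2 / median, the expected share with a PFS event is

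1 − [exp(−6λ) − exp(−18λ)] / (12λ).

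- Median 13.8: λ = 0.0502; 1 − (0.740 − 0.405)/0.603 = 0.444; × 70 = 31.1.
- Median 11.1: λ = 0.0624; 1 − (0.688 − 0.325)/0.749 = 0.516; × 70 = 36.1.
- Median 20 (assumed, for range): 0.335; × 70 = 23.5.

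A PFS event is progression or death, so each count is an upper figure for progressed patients under these assumptions.

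**5. Can the mixing be sized?** Not from the documents. Suppose 31 progressed patients, of whom 50% to 90% receive a next line, and suppose 5% to 20% of all 70 switch without recorded progression (all assumed).

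- Lowest: 3.5 / (27.9 + 3.5) = 11% of recipients fall outside the objective.
- Highest: 14 / (15.5 + 14) = 47%.

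A range this wide shows only that the amount is undetermined.

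**The case against.** **The denominator.** A reader might infer that the table uses the wrong denominator, with unprogressed patients still on first-line treatment diluting the percentages. The documents do not support this. SAP 8.3.5 plans durations by drug and states no percentage. A duration can come only from a recipient of that drug, so patients with no later treatment contribute nothing. The gap is a missing frequency by progression status, not a wrong percentage.

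**Counts may appear anyway.** SAP 7.2 includes the number of observed values among its summary statistics, and protocol 9.7.2 summarises qualitative variables by counts and percentages. The table layouts are in a separate document (SAP 1) that is not available here. Counts per drug may therefore be shown, but nothing in the plan would split them by progression.

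**Reason for switching.** A reader might also infer that patients who start a next line without recorded progression switched for toxicity. The censoring rule says only that no record exists. Protocol 9.9 acknowledges missing chart data, so some may have progressed without documentation. This stands as a reason to show these patients separately rather than drop them, and it makes the broader endpoint a defensible choice if the objective is worded to match.

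**Weight.** The objective is secondary and descriptive, and the split could still be made at analysis from data already required. This limits the seriousness but does not remove the mismatch in the written plan.

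**Conclusion.** The concern holds in this form: objective 4 is conditional on progression, its endpoint, variable and analysis are not, and SAP 8.3.5 carried out as written would not answer it. Switches without recorded progression are mixed with post-progression treatment. Neither regimen frequency among progressed patients nor the number with no further treatment is specified.

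This conclusion rests on the wording alone. The amount of mixing is unknown. The 31 to 36 of 70 is an illustration that depends on uniform entry, exponential PFS and a median borrowed from the cited trial. It should not be read as a forecast of progressed patients, since it includes deaths without progression.

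The consequence is modest, confined to one secondary objective, and cheap to repair before data lock.

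**What to change.** In SAP 8.3.5, add a table of the first subsequent regimen as n (%) by progression status:

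- **Objective 4 column.** Patients with PD recorded on or before the start of subsequent treatment, plus patients with PD and no subsequent treatment. State this group as the denominator.
- **Row for no subsequent treatment by 20 June 2021.** Split it by status: died, lost to follow-up, still on a first-line drug, other. Without the split the row would pool quite different situations.
- **Separate column for a next line started without recorded PD.** Tabulate by reason for first-line discontinuation, with a note that some of these patients may have undocumented progression.

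Keep the duration summary. Add to protocol 9.1.2 that later drugs are reported by progression status. If the sponsor intends all subsequent treatment, reword objective 4 in both documents and keep the split.

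No new data should be needed. The first progression or death date is collected under protocol 9.3.3, discontinuation reasons under 9.3.5 and 9.3.6, and the start of subsequent treatment is already required for PFS censoring. The cost is some SAP wording and one extra table with smaller cell counts.
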